#### **2. Null Hypothesis:**

There is no difference in upper extremity strength when lidocaine is used as a steroid diluent instead of saline for cervical epidural steroid injections.

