**STUDY-WIDE NUMBER OF PARTICIPANTS:**

Sample Size Calculation

Group 1: n = 60 (CESI with Lidocaine Diluent)

Group 2: n = 60 (CESI with Saline Diluent)

Group 3: n = 20 (no CESI, control group)

A power analysis was performed based upon previous observations of changes in UE strength (24,25) using Fisher's Exact Test. Sample sizes of 52 in each of the two treatment groups will achieve > 80% power to detect a group different in proportions, assuming 20% of patients in the Lidocaine group will demonstrate a motor deficit after the CESI and those in the Saline group will demonstrate no difference in motor strength after the CESI, and further assuming a 2% measurement error with the strength testing method described. The alpha level of this test statistic is set at 0.05, but the significance level actually achieved by this study design is 0.0004. To allow for drop outs, a total of 130 subjects will be enrolled in group 1 and 2. Group 3 will enroll a convenience sample of 20 control subjects based on available patients. Total of 150 subjects for the study will be enrolled.

**Statistical analysis:** The primary outcome (UE strength by dynamometry will be compared between the lidocaine and control group using Fisher's Exact Test. Secondary outcomes will be compared using the Mann-Whitney test for continuous data and a chi-squared statistic. A P <0.05 will be required to reject the null hypothesis.

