### **STUDY ENDPOINTS:**

#### **Primary outcome:**

Change in upper extremity strength defined by dynamometry measurements for each individual in each treatment group before and 30 minutes after the procedure (CESI or no CESI).

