### **PROCEDURES INVOLVED:**

#### **Study design:**

Prospective, randomized, controlled, double blinded trial in patients undergoing CESI for symptoms of cervical radiculitis.

**Group #1:** Interlaminar cervical ESI at the C7-T1 level with triamcinolone 80 mg + 2 mL 1% lidocaine (total volume 4 cc).

**Group #2:** Interlaminar cervical ESI at the C7-T1 level with triamcinolone 80 mg + 2 mL preservative saline (total volume 4 cc).

**Group #3:** Control group (No CESI) cervical or occipital facet injection

Adults who are eligible to have a CESI for treatment of cervical radiculitis at the Northwestern Anesthesiology Pain Medicine Center will be approached by authorized research personnel prior to a patient's CESI is performed and will obtain informed consent from patients who agree to participate.

A pre-procedure NRS pain score and presence of subjective or objective symptoms of UE weakness will be recorded by a blinded authorized study team member. Bilateral handgrip, wrist extension, elbow flexion, and elbow extension strength (myotomes C5-T1) will be measured prior to the injection procedure using a handheld JAMAR® PLUS+ digital dynamometer (Sammons Preston, Bolingbrook, IL) for hand grip strength and a push/pull handheld hydraulic dynamometer (Balego and Associates Inc., St. Paul, MN) for arm strength assessment. Three baseline strength measurements will be recorded for each strength test. Measurements will be taken prior to and 30 minutes following the

injection procedure. Participants will also be queried with the Upper Extremity Functional Index (UEFI) before the injection procedure and again 1 day and 1 week after the procedure (administered via telephone).

Group 1 and 2 participants will be randomized to treatment group based on a random computer-generated schedule (<https://www.randomizer.org>) and will be blinded to the group to which they are assigned. Blinding will not occur with Group 3. Providers will not be blinded to randomization; blinded research personnel will collect all outcome measures in this study.

All standard Pain Center procedures for CESIs will be followed (standard practice) including time out, skin prep, hemodynamic monitoring, image guidance, post-injection instruction etc.

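### Strength is measured continuously but planned only as a yes/no Fisher comparison; no estimate, confidence interval or baseline-adjusted comparison of strength change is prespecified

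*Combined protocol and SAP*

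**What the plan says.** The primary outcome under STUDY ENDPOINTS is on a measured scale: "Change in upper extremity strength defined by dynamometry measurements for each individual in each treatment group before and 30 minutes after the procedure". The Study design section calls for four strength tests (grip, wrist extension, elbow flexion, elbow extension) on both sides, before and 30 minutes after the procedure. It adds "Three baseline strength measurements will be recorded for each strength test", and any weakness present beforehand is also recorded.

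The Statistical analysis paragraph, under STUDY-WIDE NUMBER OF PARTICIPANTS, names one test for this outcome: "The primary outcome (UE strength by dynamometry will be compared between the lidocaine and control group using Fisher's Exact Test". I read the comparator as the saline arm, because the null hypothesis is "There is no difference in upper extremity strength when lidocaine is used as a steroid diluent instead of saline" and the sample size compares those two arms. For the rest, "Secondary outcomes will be compared using the Mann-Whitney test for continuous data and a chi-squared statistic". The secondary outcomes listed are mean arterial pressure, heart rate, NRS pain, UEFI and complications; strength is not among them.

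The sample size is built on proportions, "assuming 20% of patients in the Lidocaine group will demonstrate a motor deficit after the CESI". The comparison arm is taken to show no change in strength, and an error of 2% in the readings is allowed for. No cut-off for a motor deficit is given, and no mean loss or SD.

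**The concern.** The research question, the null hypothesis and the stated hypothesis are about strength, not about the share of patients past a threshold. The Background says that even slight weakness could be dangerous and that the answer bears on post-procedure instructions. A yes/no rule with a low false-positive rate is poorly suited to a loss that is modest in each patient but shared by most of them, because few patients cross the threshold.

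A non-significant Fisher result could then be reported as no difference in strength, with nothing to show how large a loss the data exclude. A continuous analysis chosen after the data are seen, from four tests on two sides, would be open to selection. This gap is separate from the missing deficit definition: a clear yes/no rule would make Fisher's test workable but would still give no estimate of strength loss.

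**Working it through.** **1. The plan's own figure.** Inputs from the sample-size paragraph: 52 per arm, 20% deficit on lidocaine, 2% measurement error, alpha 0.05. Taking the 2% as the saline deficit rate and summing the binomial probabilities of all 2×2 tables that a two-sided Fisher test rejects:

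- Power at 20% v 2% is 80.3%, and 52 is the smallest number per arm that reaches 80%.
- The actual size at 2% v 2% is 0.00042.

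These match the stated power above 80% and achieved level of 0.0004. At 20% v 0% the power would be 96.3%. Using 2% as the saline rate is therefore an inference, but it reproduces both stated figures.

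**2. Loss spread across all patients.** Assumptions not in the documents: change scores are normal with SD 1, lidocaine shifts every patient down by d SD, and the cut-off gives saline deficit rate p0. Then:

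- Lidocaine deficit rate: p1 = Φ(Φ⁻¹(p0) + d). For p0 = 2% and d = 0.555, p1 = Φ(−2.054 + 0.555) = 6.7%.
- Fisher power: the enumeration in step 1, with p1 and p0.
- Comparison of means: two-sample t test, 102 df, noncentrality d × √(52/2). For d = 0.555 this is 2.83, giving 80% power; for d = 0.8 it is 4.08, giving 98%.

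| Loss d | Saline rate p0 | Lidocaine rate p1 | Fisher power | Means power |
|---|---|---|---|---|
| 0.555 SD | 2% | 6.7% | 5.5% | 80% |
| 0.555 SD | 5% | 13.8% | 20% | 80% |
| 0.555 SD | 10% | 23.4% | 35% | 80% |
| 0.8 SD | 2% | 10.5% | 24% | 98% |
| 0.8 SD | 5% | 19.9% | 53% | 98% |
| 0.8 SD | 10% | 31.5% | 73% | 98% |

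The first row shows the mechanism. With 52 per arm and no saline deficits, Fisher's test needs at least 6 lidocaine deficits to reject; the expected number is 0.067 × 52 = 3.5. With a 2% saline rate, a uniform loss must reach about 1.21 SD to produce the planned 20%.

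**3. Loss concentrated in a minority.** Choose the responder fraction f so that the lidocaine deficit rate is 20% against 2%: f = 0.18 / (Φ(−2.054 + L) − 0.02), where L is each responder's loss in SD. Fisher power is 80% throughout. Simulated Welch t test, 52 per arm:

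| L | f | Means power |
|---|---|---|
| 2.5 SD | 28% | 79% |
| 3 SD | 22% | 72% |
| 4 SD | 19% | 74% |
| 5 SD | 18% | 81% |
| 6 SD | 18% | 86% |

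**4. What an interval would add.** If the SD of change is equal in the two arms, the 95% CI for the difference in mean change has half-width about 1.98 × √(2/52) = 0.39 SD. The planned report contains no corresponding statement.

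**The case against.** The strongest reply is that the plan does not expect a general loss. Its 20% assumption, and the Background's remark that a small share of patients have motor block after low-dose transforaminal injection, both point to a minority of responders. Advice after the procedure also turns on how many patients become weak. That stands: in this pattern the means comparison is no better than Fisher's test over much of the range (72 to 74% against 80% at 3 to 4 SD). A reader might infer that Fisher's test is the wrong primary test; the documents do not support that.

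The size of the contrast also depends on the undefined cut-off. A 2% saline rate is the strictest of the three shown, and the gap narrows as the rate rises. A reader might infer that general weakness would certainly go undetected; power is low but not zero, so probably missed is as far as this goes. Nor can 0.555 SD be called moderate weakness: with no SD in the documents, it could be clinically trivial.

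A reader might also infer that baseline is ignored. It is not, because the endpoint is each person's change. The narrower gap is the lack of a continuous between-group estimate adjusted for baseline. Such adjustment usually adds precision; it is not guaranteed to.

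None of this supplies the missing estimate or interval.

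**Conclusion.** The point holds as a gap in what will be estimated, not as a fault in the primary test, whose stated power and size reproduce. Strength is measured continuously, the only analysis named for it is a yes/no test, and no between-group estimate, confidence interval or baseline-adjusted comparison is planned.

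For a loss shared by all patients, Fisher power is 5.5 to 35% at 0.555 SD and 24 to 73% at 0.8 SD, against 80% and 98% for a comparison of means. For a loss confined to 18 to 28% of patients, the two approaches are close. The SD units, normality, the shape of the loss and the 5% and 10% saline rates are assumptions. The absence of an estimate and interval does not depend on them. The continuous analysis should therefore support Fisher's test, not replace it.

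**What to change.** Keep Fisher's test as primary at its current alpha, and report the deficit rates with the risk difference and its 95% CI beside the P value.

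Add to the Statistical analysis paragraph one prespecified supportive analysis of lidocaine versus saline:

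- **Model:** a single mixed model over the eight strength measures (four tests, two sides), with a patient random effect and terms for test and side.
- **Outcome:** 30-minute strength as a percent of the mean of the three baseline readings for that test and side. A zero reading remains usable on this scale. The plan should state how many readings are taken at 30 minutes and, if more than one, use their mean.
- **Adjustment:** that baseline mean and recorded pre-procedure weakness.
- **Report:** the difference in percentage points with 95% CI, plus the same estimate for each test descriptively, so that a deficit in one myotome is not averaged away.

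The cost is one paragraph of analysis wording and a little analysis time, with no new data, patients or alpha. The downside is a second strength result that may disagree with the primary test, so it must be labelled supportive.

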## **OBJECTIVES:**

### **1.0 Research Aims:**

#### **1. Research Question:**

Is there a detectable difference upper extremity strength as measured with dynamometry after cervical epidural steroid injections when lidocaine is used instead of saline as a steroid diluent in patients with cervical radiculitis?

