## **BACKGROUND:**

### **Literature:**

Cervical radicular pain is a common problem that is often treated by epidural steroid injection (1). While clinical practice guidelines do not specifically recommend or discourage the use of local anesthetic in the epidural injectate (2), the majority of the published literature on clinical outcomes of cervical epidural steroid injection includes the use of lidocaine in the epidural injectate (3-11). Consequently, many practitioners elect to use local anesthetic in the epidural injectate in order to provide immediate pain relief to patients in cases of exquisitely painful radicular symptoms. Local anesthetic may also be used in such cases to gain additional clinical information regarding a patient's analgesic response, which may help pinpoint a precise anatomic source of pain when the clinical presentation and pain generator is not clear.

Local anesthetic injection into the epidural space has the potential to cause transient weakness of the upper extremities. High doses of local anesthetic in the cervical epidural space (12) and inappropriately placed low-dose local anesthetic in the subdural space or subarachnoid space (13,14) are known to cause motor weakness.

Appropriately placed, low-dose local anesthetic injected into the epidural space via a transforaminal approach, in close proximity to the exiting spinal nerve root, causes motor block in a small proportion of patients (15). However, the effect of low-dose injection of local anesthetic in the cervical interlaminar epidural space on objective upper extremity strength has not been well characterized in the published literature.

This proposition affects post-procedure instructions, as even mild weakness may pose a hazard during performance manual activities that require the upper extremity/extremities such as using a handrail or cane handle for support.

Dynamometry is an established method for assessing muscle strength and motor neuron function with high reliability, and has been used to objectively assess changes in upper extremity strength and has been validated in several patient populations (16-22).

This study aims to determine whether a standard dose of 2 mL 1% lidocaine vs 2mL of saline included as a steroid diluent in a C7-T1 cervical interlaminar epidural steroid injection (CESI) causes an objective change in strength as measured by dynamometry.

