### **INCLUSION AND EXCLUSION CRITERIA:**

Patients who plan to undergo CESI for treatment of cervical radiculitis or the control group (no CESI) will be screened for eligibility by authorized research personnel during their visit to the Northwestern Anesthesiology Pain Medicine Center, [name], Lavin Pavilion.

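### The primary-analysis sentence compares lidocaine with the control group, a label the protocol gives only to the non-randomised Group 3; it should name Group 2 (saline)

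*Combined protocol and SAP*

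**What the plan says.** The only sentence on the primary test is in the statistical analysis paragraph under STUDY-WIDE NUMBER OF PARTICIPANTS. It says that upper extremity strength "will be compared between the lidocaine and control group", using Fisher's Exact Test.

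Control, as the name of a group, belongs to Group 3 throughout:

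- The sample-size list, just above that sentence, has "Group 3: n = 20 (no CESI, control group".
- The same section adds that "Group 3 will enroll a convenience sample of 20 control subjects based on available patients".
- The opening of INCLUSION AND EXCLUSION CRITERIA refers to "the control group (no CESI".
- The heading of the Group 3 eligibility criteria and the Group 3 entry under Study design use the same label.

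Group 2 is identified by its number or by its saline diluent and is never called control. The one other related use, in Study design, describes the trial as controlled and labels no group.

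The aims point to saline. The research question asks about strength "when lidocaine is used instead of saline as a steroid diluent in patients with cervical radiculitis". The null hypothesis concerns strength "when lidocaine is used as a steroid diluent instead of saline for cervical epidural steroid injections". The Background sets out to compare "a standard dose of 2 mL 1% lidocaine vs 2mL of saline". The power statement assumes that "those in the Saline group will demonstrate no difference in motor strength after the CESI". Under PROCEDURES INVOLVED, only Groups 1 and 2 are randomised.

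**The concern.** In the protocol's own vocabulary, the primary test is Group 1 against Group 3. Group 3 patients are not randomised, have no epidural injection, and receive bupivacaine and methylprednisolone instead of triamcinolone with lidocaine or saline. That contrast does not isolate the diluent, and with 20 comparator patients it has far less power than the trial was sized for.

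The literal reading could be carried out. The primary outcome under STUDY ENDPOINTS covers patients with and without an epidural injection, so Group 3 will have primary-outcome data. Two comparisons would then be available after the data are in, and the sentence that should settle which one is primary names the wrong group. No other sentence gives Group 3 a role in the analysis.

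**Working it through.** **Inputs, all from STUDY-WIDE NUMBER OF PARTICIPANTS.** Lidocaine deficit rate 20%; no true deficit on saline; 2% measurement error; 52 per arm for power above 80%; alpha 0.05; achieved level 0.0004; listed sizes 60, 60 and 20; 130 enrolled in Groups 1 and 2.

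**Assumptions.**

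- The 2% measurement error is read as a 2% observed deficit rate on saline.
- The test is two-sided; the plan does not say.
- Equal allocation gives 130/2 = 65 per arm.
- The documents give no deficit rate for Group 3, so 2% and 0% are used to match the saline cases.

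**Method.** Let a of n₁ lidocaine patients and b of n₂ comparator patients have a deficit. The two-sided Fisher p(a, b) sums the hypergeometric probabilities, given the margins, of all tables no more probable than the one observed. Then

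power = Σₐ Σ_b Bin(a; n₁, 0.20) × Bin(b; n₂, p₂) × 1[p(a, b) ≤ 0.05].

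The achieved level is the same sum with p₂ as the rate in both arms.

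**Step 1: the plan's own figures.** With n₁ = n₂ = 52 and p₂ = 0.02, power is 0.803 and the achieved level is 0.00042, which match the stated values. Of the sizes from 44 to 55 per arm that were tried, 52 is the smallest to reach 80% (51 gives 0.791). The calculation was therefore done for lidocaine against saline.

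**Step 2: the same test against each possible comparator.**

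| Lidocaine n | Saline, equal n, 2% | Group 3, n = 20, 2% | Saline, equal n, 0% | Group 3, n = 20, 0% |
|---|---|---|---|---|
| 52 | 80.3% | 33.8% | 96.3% | 47.2% |
| 60 | 87.8% | 39.0% | 98.8% | 55.1% |
| 65 | 91.1% | 39.0% | 99.4% | 54.9% |

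At 2% in both groups, the achieved level against Group 3 would be 0.0028 (52 vs 20), 0.0048 (60 vs 20) or 0.0046 (65 vs 20). None of these is the stated 0.0004.

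**Step 3: can the choice change the result?** Take 12/60 deficits on lidocaine (the planned 20%) and hold the comparator rate equal.

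| Comparator rate | Against saline | Against Group 3 |
|---|---|---|
| 5% | 3/60, p = 0.025 | 1/20, p = 0.17 |
| 0% | 0/60, p = 0.0003 | 0/20, p = 0.031 |

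At 5% the two tests fall on opposite sides of 0.05. With no comparator events, both are significant.

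**The case against.** The strongest reply is that the paragraph largely corrects itself. It ends by setting the P value needed to reject the null hypothesis, and the protocol has only one, which concerns lidocaine in place of saline. A test against Group 3 cannot reject it. The trial is also described as randomised and controlled, and only Groups 1 and 2 are randomised, so saline is the control arm in the ordinary sense. This stands as evidence of intent, and most readers of the whole protocol would choose saline. It does not repair the sentence, because the same section attaches the label to Group 3 a few lines earlier.

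A second reply is that the Group 3 power figures describe an analysis nobody plans and rest on deficit rates the documents do not give. That is fair. They show what the literal wording would cost and that the stated power does not belong to it; they do not forecast the trial's performance.

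A reader might go further and infer that the sponsor intends a non-randomised primary comparison, or that the trial is too small. The documents support neither: hypothesis, randomisation and power agree on saline, and the sample size reproduces. Nor does the lack of blinding in Group 3 show that its outcomes are assessed unblinded, since Study design says blinded personnel collect all outcome measures.

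**Conclusion.** The sentence is wrong as written: it names as primary comparator a label the protocol reserves for Group 3, when the intended comparator is Group 2. It is an error of labelling in the analysis rule, not a fault in the randomised design or the sample size.

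Followed literally, the rule would replace a randomised comparison with 80–91% power (saline at 2%) or 96–99% (saline at 0%) by a non-randomised one with 34–39% or 47–55%. These figures rest on the stated 20% lidocaine rate, the reading of the measurement error, and assumed Group 3 rates. The choice can change the conclusion but need not, as the zero-event case shows.

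A reader might also infer that, once the comparator is named, the primary test is fully specified. The documents do not support that. The primary outcome is a change in dynamometry strength, measured on both sides at four sites, and no threshold is given for the yes/no motor deficit that Fisher's test needs. The counts above are illustrative for that reason too. The correction should be made before the data are analysed.

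**What to change.** In the statistical analysis paragraph, replace the reference to the lidocaine and control group with: Group 1 (lidocaine) and Group 2 (saline). Add one sentence saying that Group 3 is not part of the primary test. The sponsor should then state what Group 3 is for, whether a secondary comparison or a descriptive summary; the documents do not settle this, so the wording is the sponsor's to choose.

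The cost is one replaced phrase and a short addition. The arms, sample size, data collection and choice of test do not change.

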**STUDY-WIDE RECRUITMENT METHODS: N/A**

## **MULTI-SITE RESEARCH: N/A**

### **STUDY TIMELINES:**

Each enrolled subject will receive a follow up telephone call 24 hours and one week after the procedure. The anticipated duration for study enrollment is 6 months.

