#### **Secondary outcomes:**

Mean arterial pressure

Heart rate

Numeric Rating Scale (NRS) pain score

Upper Extremity Functional Index (UEFI) score

Procedure complications

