Group 1 and Group 2 group randomization, triamcinolone acetonide 80 mg (Kenalog, E. R. Squibb & Sons Limited, Uxbridge UK) will be combined with 2mL Lidocaine 1% or 2 mL preservative free saline and will be injected during the CESI procedure. In all cases, the total injectate volume will be 4 mL. All injections will be performed with fluoroscopy guidance (current standard practice).

Group 3 will receive standard treatment intramuscular injection of bupivacaine .25% 10-20 mL and methylprednisolone 20 mg.

All participant's will be recovered for approximately 20 minutes following the procedure ( and will be discharged from the clinic with standardized written discharge instructions given to all patients who receive an injection in this practice (includes bathing instructions, activity following the procedure, signs and symptoms of neurologic compromise, for example).

All participants will contacted by telephone by authorized study team member on Day 2 and again 1 week after the procedure (CESI or No CESI) to assess for residual subjective weakness in the hands or arms as well as any other adverse reactions. As the clinical duration of effect for 1% lidocaine is 1-2 hours in most patients, we do not expect to see sustained subjective weakness at 24 hour and 1 week post-CESI assessments as a result of this diluent. As above, the Upper Extremity Functional Index will be administered.

Group 1 and 2 participants will only be recruited for this study for a single CESI. Those who require repeat injections will not be recruited for this study a second or third time.

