**RESOURCES AVAILABLE:**

The research study team will be fully informed about the research protocol. Copies of the protocol will be available for review in the Pain Center. After enrollment, the study will be conducted in Pain Center. Research study team will collect procedure and post procedure data. The follow up will be by telephone at 24 hours and again 1 week following the procedure (CESI and Non CESI).

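### UEFI is compared by an unadjusted Mann-Whitney test that leaves the collected baseline score unused and plans no effect interval; baseline-adjusted ANCOVA with a 95% CI is a cheap improvement

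*Combined protocol and SAP*

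**What the plan says.** The whole analysis plan for secondary outcomes is in the Statistical analysis paragraph under STUDY-WIDE NUMBER OF PARTICIPANTS: "Secondary outcomes will be compared using the Mann-Whitney test for continuous data and a chi-squared statistic". A threshold of P below 0.05 follows. No covariate, effect estimate or confidence interval is mentioned.

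Under STUDY ENDPOINTS, the secondary outcome is listed only as "Upper Extremity Functional Index (UEFI) score". The primary outcome, by contrast, is defined as a change. UEFI is not named in the analysis paragraph, but Mann-Whitney is the only stated method that fits a score.

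Under PROCEDURES INVOLVED, participants complete the "Upper Extremity Functional Index (UEFI) before the injection procedure and again 1 day and 1 week after the procedure". A baseline value is therefore available for the analysis. Only Groups 1 and 2 are randomised.

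**The concern.** A two-sample Mann-Whitney test uses one number per participant. If that number is the follow-up score, the baseline is discarded. If it is the change, the baseline is subtracted in full however weakly it predicts follow-up. Neither is generally the most precise use of a baseline, and the plan does not say which applies.

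The missing interval matters because a null result is plausible. On the later assessments the protocol says "we do not expect to see sustained subjective weakness at 24 hour and 1 week post-CESI assessments". That sentence concerns subjective weakness rather than UEFI, so a null UEFI result is an inference from it, but a reasonable one. A non-significant P value does not show how large a functional loss the data exclude. An interval does, and its width then decides how informative the result is.

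**Working it through.** **1. The plan's own figure.** The only sample-size statement concerns the primary outcome: "Sample sizes of 52 in each of the two treatment groups will achieve > 80% power to detect a group different in proportions". Exact enumeration of the two-sided Fisher test with 52 per arm, 20% against 2%, gives power 80.3%. The rejection probability when both rates are 2% is 0.00042, which matches the stated 0.0004. The figure reproduces, and nothing below changes it. No power, SD or target difference is stated for UEFI.

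**2. Inputs for UEFI.** Taken from the documents: 52 per arm. Assumed: all 52 give complete pairs; equal SD at baseline and follow-up; correlation rho = 0.3, 0.5, 0.7. Results are in SD units.

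**3. Relative variance.**
- ANCOVA against follow-up only: 1 − rho² = 0.91, 0.75, 0.51.
- ANCOVA against change: (1 + rho)/2 = 0.65, 0.75, 0.85.

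**4. 95% CI half-width for a difference in means, 52 per arm.**

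| Analysis | Formula | rho 0.3 | rho 0.5 | rho 0.7 |
|---|---|---|---|---|
| Follow-up only | 1.96 × √(2/52) | 0.384 | 0.384 | 0.384 |
| Change | 1.96 × √(4(1 − rho)/52) | 0.455 | 0.384 | 0.298 |
| ANCOVA | 1.96 × √(2(1 − rho²)/52) | 0.367 | 0.333 | 0.275 |

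Change is less precise than follow-up below rho 0.5 and more precise above it. ANCOVA is narrowest throughout, but by only 0.384 − 0.367 = 0.017 SD against follow-up at rho 0.3.

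**5. Does this survive against rank-based intervals and non-normal data?** Simulated median half-widths with no true effect, 52 per arm, at rho 0.3 / 0.5 / 0.7. Ceiling data are integer scores with SD 18 before cutting at 0 and 80, and 18 is the unit; all of this is assumed.

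| Data | Hodges-Lehmann, follow-up | Hodges-Lehmann, change | ANCOVA |
|---|---|---|---|
| Normal | 0.40 / 0.40 / 0.40 | 0.47 / 0.40 / 0.31 | 0.37 / 0.34 / 0.28 |
| Ceiling, about 12% at the top | 0.36 / 0.36 / 0.36 | 0.42 / 0.36 / 0.28 | 0.34 / 0.31 / 0.255 |
| Ceiling, about 28% at the top | 0.25 / 0.25 / 0.25 | 0.36 / 0.28 / 0.22 | 0.29 / 0.27 / 0.22 |
| Residuals t, 3 df | 0.31 / 0.33 / 0.36 | 0.41 / 0.33 / 0.24 | 0.34 / 0.31 / 0.255 |

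At 28% at the top, the rank interval on follow-up is narrower at rho 0.3 and 0.5. With t residuals it is narrower on follow-up at 0.3, and on change at 0.7.

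**6. Power for an assumed 0.5 SD shift** (4000 simulated trials, 52 per arm, rho 0.3 / 0.5 / 0.7).

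| Data | Mann-Whitney, follow-up | Mann-Whitney, change | ANCOVA |
|---|---|---|---|
| Normal | 0.69 / 0.69 / 0.70 | 0.54 / 0.69 / 0.89 | 0.75 / 0.82 / 0.94 |
| Ceiling, about 28% at the top | 0.67 / 0.67 / 0.67 | 0.53 / 0.67 / 0.87 | 0.71 / 0.78 / 0.91 |
| Residuals t, 3 df | 0.89 / 0.85 / 0.78 | 0.68 / 0.85 / 0.98 | 0.79 / 0.86 / 0.94 |

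Under the heavy ceiling, ANCOVA power is not below that of either unadjusted test. With t residuals a rank test can have clearly more power (0.89 against 0.79 at rho 0.3). Type I error stayed between 0.043 and 0.060 over all settings simulated for power (Monte Carlo SE 0.0034).

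**The case against.** The best defence is that Mann-Whitney is valid here and needs no normality, whereas ANCOVA moves the target to a mean difference under a linear model for a bounded score. The documents give no UEFI distribution, correlation, range, margin or hypothesis, so the gain rests wholly on assumptions. All of that stands. It limits the point to an optional improvement and is the reason to keep a rank-based analysis alongside. It does not explain leaving a collected baseline unused.

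It can also be said that a rejection threshold does not forbid reporting estimates. That is true: the plan is silent on intervals and does not exclude them. But no other section supplies one.

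Two stronger readings are tempting and fail. First, a reader might infer that adjustment always narrows the interval for a ceiling-limited score. It did at about 12% at the top, but not at about 28%. At 34% the Hodges-Lehmann follow-up interval was 0.19 SD against 0.27, 0.25 and 0.21 for ANCOVA. The two intervals estimate different quantities, so width alone does not settle the choice.

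Second, a reader might infer a conflict in the timing of the first follow-up, because participants are to be "contacted by telephone by authorized study team member on Day 2 and again 1 week after the procedure", while STUDY TIMELINES has "Each enrolled subject will receive a follow up telephone call 24 hours and one week after the procedure" and RESOURCES AVAILABLE has "The follow up will be by telephone at 24 hours and again 1 week following the procedure". The documents do not support a conflict. The sentence after the Day 2 wording calls the same contacts the 24 hour and 1 week assessments, and the privacy section agrees. Day 2 is simply the day after a procedure on Day 1.

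**Conclusion.** The point holds as a low-priority improvement. The planned UEFI comparison is valid but ignores the baseline already collected and plans no effect interval. With 52 complete pairs per arm and under normality, adjustment brings the 95% CI half-width to 0.37, 0.33 or 0.27 SD at rho 0.3, 0.5 or 0.7. The gain over follow-up alone runs from negligible to about a quarter of the width (0.27/0.38 = 0.71).

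This depends on the assumed correlation, complete follow-up and the shape of the scores. With heavy-tailed residuals the rank test can have more power. With about 28% or more at the top the Hodges-Lehmann interval can be narrower, although baseline-adjusted power stays at least about equal. There is no bias, and no effect on the primary Fisher test or the sample size.

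**What to change.** Add to the Statistical analysis paragraph that, for UEFI at 1 day and at 1 week, Group 1 will be compared with Group 2 by ANCOVA of the follow-up score adjusted for baseline UEFI, and that the adjusted difference will be reported with its 95% CI.

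Add one rank-based sensitivity analysis. It can be a baseline-adjusted rank ANCOVA, which keeps nearly all of the power gain, or a Mann-Whitney test with a Hodges-Lehmann shift and 95% CI. For the latter, state before data are seen whether it ranks follow-up or change.

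The cost is two or three sentences and trivial analysis time, with no new data or visits and no change in sample size. The downside is reliance on a linear model for a bounded score, and the sensitivity analysis covers that.
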